## **2. STUDY DETAILS**

### **2.1. Study Objectives**

The study is comprised of 5 Parts.

- Part 1 enrolls symptomatic subjects with recurrent idiopathic pericarditis (RIP) with an elevated marker of systemic inflammation (C-reactive protein [CRP]  $> 1\text{mg/dL}$ ).
- Part 2 enrolls symptomatic subjects with RIP with CRP  $\leq 1\text{ mg/dL}$  which, in the opinion of the investigator, can be attributed to concomitant medications (e.g., corticosteroids) and with pericardial inflammation present on cardiac magnetic resonance imaging (MRI) confirmed by the imaging core lab.
- Part 3 enrolls subjects with corticosteroid-dependent RIP not experiencing symptoms which would meet the diagnostic criteria for a flare of pericarditis.
- Part 4 enrolls symptomatic subjects with recurrent post pericardiotomy syndrome (PPS) with an elevated marker of systemic inflammation (CRP  $> 1\text{mg/dL}$ ).
- Part 5 enrolls subjects with corticosteroid-dependent recurrent PPS not experiencing symptoms which would meet the diagnostic criteria for a flare of pericarditis.

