**2.1.3. Primary Objective for Parts 3 and 5**

- To evaluate feasibility of weaning from corticosteroids while receiving KPL-914 in subjects with corticosteroid-dependent RIP or recurrent PPS.

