**2.2. Study Design**

This is an open-label single-active-arm pilot study to explore clinical and biochemical endpoints of improvement of pericarditis symptomatology and to collect inter- and intra-subject variability data on both at-baseline and on-treatment parameters. This study consists of 5 distinct Parts, and all subjects will be treated with once-weekly subcutaneously (SC)-administered injections of KPL-914.

**Prescreening Period:** Prior to enrollment, potential subjects may enter an optional prescreening period, after signing a Prescreening ICF (or prescreening informed assent, if applicable), to confirm the diagnostic workup and to allow monitoring for symptoms and inflammatory markers (CRP, ESR, etc) while concomitant pericarditis medications may be managed by the Investigator or their clinician according to standard of care.

**Screening Period:** The Screening Period starts with the signing of the full study ICF (or informed assent form, if applicable) (SCV1) and may last for up to 3 days (72 hours) until SCV2. At SCV1, baseline subject and disease characteristics will be determined. At Screening Visit 2 [SCV2]), within the 24 – 72 hour period before subjects advance to the Treatment Period of the study, additional laboratory samples may be drawn to provide additional baseline reference data.

Under special circumstances, the Investigator in consultation with the Sponsor can combine SCV1 and SCV2. The end of the Screening Period coincides with the start of the Treatment Period (Day 0 Visit). For this reason, not all subjects will have all 3 visits SCV1, SCV2 and Day 0.

At the SCV1, subjects will be given a medication diary to record administration of pericarditis medications and rescue (pain) medication use during the Screening Period.

Patient-reported pericardial pain evaluations will be performed on-site at SCV1 and SCV2 using a validated 11-point NRS instrument. A patient-reported QoL questionnaire will be administered as well.

**Treatment Period:** The first dose of Study Drug will be administered to subjects at the Study site/Clinic at Visit 1 on Day 0. During this visit, subjects and/or caregivers will be trained for outpatient drug administration. At Day 3, the Investigator (or designee) telephone call/virtual visit will occur to evaluate safety (AE evaluations) and patient-reported pericardial pain using a validated 11-point NRS instrument.

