##### **4.2. Primary Efficacy Endpoints for Parts 3 and 5**

Primary efficacy endpoint will be disease activity after corticosteroid taper in subjects with corticosteroid dependent RIP or recurrent PPS.

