### **5. STATISTICAL METHODOLOGY**

#### **5.1. General Considerations**

All statistical evaluations will be conducted using SAS® version 9.4 or higher (SAS® Institute, Cary, North Carolina). All tables, figures and listings will be produced in landscape format.

Because of the small sample size no inferential statistical analyses or hierarchical testing are planned. Analysis will be descriptive in nature.

Each Part will be analyzed separately. Tables will have columns corresponding to or be stratified by study Parts. Select analyses, as specified in further sections, will be performed for pooled groups of Parts 1, 2 and 4 and Parts 3 and 5, representing similar RIP and PPS populations, i.e. symptomatic and asymptomatic-CS dependent subjects. In general, all data will be listed by study part, subject and visit/time point where appropriate. The total number of subjects under the stated population (N) will be displayed in the header of summary tables.

Data will be summarized using descriptive statistics for continuous variables. Unless otherwise specified, descriptive statistics will include number of subjects, mean, standard deviation, minimum, median and maximum. In case of  $n < 2$ , where  $n$  indicates the number of evaluable subjects at the particular time point, the standard deviation will not be calculated.. The statistic “Missing” will also be presented as the number of missing entries/subjects, if any

at that visit/timepoint, and presented as a summary statistic only when non-zero. The minimum and maximum statistics will be presented to the same number of decimal places as the original data. The mean and median will be presented to one more decimal place than the original data, whereas the standard deviation will be presented to two more decimal places than the original data.

In summary tables of categorical variables, counts and percentages will be used. The count [n] indicates the actual number of subjects with a particular value of a variable or event, which should always be less than or equal to the total number of subjects with non-missing value of the variable or event [M]. Percentage will be obtained by:  $\% = (n/M)*100$ . Unless otherwise stated, all percentages will be expressed to one decimal place.

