#### **5.4.9.8. Prednisone Use**

The following characteristics of prednisone use throughout the study will be summarized descriptively. Prednisone use will be identified via medical review of baseline and concomitant medications.

- Daily dose of prednisone at study baseline (mg/day) in subjects who were treated with study drug in TP and who were taking prednisone at baseline
- Daily dose of prednisone at the start of extension period (mg/day) in subjects who were treated in EP with study drug and received prednisone at EP start
- For each subject with prednisone use at baseline, the subject's average daily dose in the Treatment Period (mg/day), defined as total cumulative dose of prednisone taken in the Treatment Period divided by the duration of the Treatment Period in days. For the purposes of this analysis the Treatment Period ends on the day of Week 6/End of Trial/Visit 7 for subjects who proceed to the Extension Period; for subjects who do not enter the Extension Period, the Treatment Period ends on the day of the last study drug dose.
- For each subject with prednisone use at the start of the extension period, the subject's average daily dose in the Extension Period (mg/day), defined as total cumulative dose of prednisone taken in the Extension Period divided by the duration of treatment in the Extension Period in days. For the purposes of this analysis the Extension Period starts on the day of Week 6/End of Trial/Visit 7.
- For each subject with prednisone use at baseline, the subject's average daily dose in the Treatment and Extension Periods combined (mg/day), defined as total cumulative dose of prednisone taken in both the Treatment and Extension Periods

divided by the duration of periods in days (from the first dose in the Treatment Period to the last dose in the Extension Period).

This analysis will be performed by study part, but also for pooled groups of Parts 1, 2 and 4 and Parts 3 and 5.

To evaluate disease activity after discontinuation of corticosteroids, selected efficacy parameters including CRP will be analysed in subjects who received prednisone at baseline and discontinued it by the end of EP.

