#### **5.4.9.10. Recurrent episodes of RIP and PPS during the study**

The numbers of subjects with recurrent pericarditis episodes will be summarized by the number of recurrent episodes during the study. Duration-adjusted number of episodes will be defined for each subject as the number of recurrent episodes during the study divided by the study duration (from the first dose of the study drug to study completion/discontinuation) in years. Duration-adjusted number of episodes will be summarized descriptively. This analysis will be performed for the mITT population.

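### The Parts 3 and 5 primary endpoint names no outcome, and the only analysis tied to it uses an open list of parameters in subjects who succeeded in stopping prednisone

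*SAP*

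**What the plan says.** For Parts 3 and 5 the objective in SAP Section 2.1.3 is "To evaluate feasibility of weaning from corticosteroids while receiving KPL-914 in subjects with corticosteroid-dependent RIP or recurrent PPS". Section 4.2 turns this into an endpoint: "Primary efficacy endpoint will be disease activity after corticosteroid taper in subjects with corticosteroid dependent RIP or recurrent PPS". It gives no measure, cut-off, time point or summary statistic.

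Section 5.4.9.8 (Prednisone Use) first lists prednisone dose summaries. Its last sentence, the only analysis text that takes up disease activity after corticosteroids, says that "selected efficacy parameters including CRP will be analysed in subjects who received prednisone at baseline and discontinued it by the end of EP". CRP is the one parameter named.

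Recurrence is handled separately, in Section 5.4.9.10: "The numbers of subjects with recurrent pericarditis episodes will be summarized by the number of recurrent episodes during the study". The duration-adjusted count there runs from first dose to completion or discontinuation, in the mITT population. It has no window after the taper and no link to Section 4.2.

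On design, Section 2.2 states "This is an open-label single-active-arm pilot study", and Section 5.1 states "Because of the small sample size no inferential statistical analyses or hierarchical testing are planned".

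**The concern.** Parts 3 and 5 ask whether corticosteroids can be withdrawn on KPL-914 without the disease returning. Section 2.1 defines these subjects at entry by the absence of a flare; for Part 5 it says "Part 5 enrolls subjects with corticosteroid-dependent recurrent PPS not experiencing symptoms which would meet the diagnostic criteria for a flare of pericarditis", and Part 3 is defined likewise for RIP. The natural answer has two components: did the subject come off corticosteroids, and did the pericarditis stay away.

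Section 5.4.9.8 secures neither.

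- **Open list.** The parameters are left to a selection with no stated author, date or rule. In an open-label study the results are visible as they accrue. Recurrence need not be among those selected.
- **Restricted set.** The analysis keeps only subjects who achieved the first component. A subject whose disease returned during the taper, and who therefore stayed on prednisone, is absent from the analysis of disease activity.

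At stake is the weaning conclusion of the pilot, which could be drawn from a favourable subset on whichever parameters look best.

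**Working it through.** **Step 1. Is a measure assigned to the endpoint anywhere else?** The SAP defines these candidates:

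| Section | Measure | Assigned to the Parts 3 and 5 primary endpoint? |
|---|---|---|
| 5.4.9.1 | CRP, with cut-offs of 0.5 and 1 mg/dL | Named in 5.4.9.8, no cut-off or visit |
| 5.4.9.2 | Effusion on echocardiogram | No |
| 5.4.9.3 | Pain NRS, with cut-off of 1 | No |
| 5.4.9.4 | Rub, ECG signs, fever | No |
| 5.4.9.5 | MRI (optional in Parts 3 and 5) | No |
| 5.4.9.6 | PROMIS scores | No |
| 5.4.9.9 | Corticosteroids stopped | No (measures weaning, not activity) |
| 5.4.9.10 | Recurrent episodes | No |
| 5.4.9.11 | Clinical Response: NRS of 2 or less with CRP of 0.5 mg/dL or less | No |

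Two CRP cut-offs and two NRS cut-offs (1 in 5.4.9.3, 2 in 5.4.9.11) give 2 × 2 = 4 possible CRP/NRS definitions of low activity, before any choice of visit. Only one pairing is predefined, as Clinical Response, and it is not linked to this endpoint. By contrast, the Parts 1, 2 and 4 primary endpoint has a model, data set and SAS code (Sections 5.4.9.1 and 8.2).

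**Step 2. Who is in the Section 5.4.9.8 set?** A subject must have been on prednisone at baseline and off it by the end of the EP. Under Section 2.2, corticosteroid tapering is encouraged in the EP, which is offered only to subjects considered treatment responders. Treatment failures may be withdrawn from study drug and are then followed for safety for the rest of the 6 weeks. Three groups can therefore fall outside the set: subjects who never entered the EP, subjects who entered but could not stop, and subjects who flared and were still on or back on prednisone at the end. Read literally, the sentence also covers prednisone only, whereas Section 4.2 speaks of corticosteroids.

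**Step 3. Direction of the restriction.** Let n be the subjects on corticosteroids at baseline, d those who stopped, and q those who stopped and had no recurrence. Then q ≤ d ≤ n, so q/d ≥ q/n. For the question of the objective, the discontinuers-only proportion can never be the lower of the two.

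**Step 4. Size, with assumed counts.** The SAP gives no numbers by Part (Section 3.1 gives only approximately up to 40 subjects across all Parts). Assume n = 8, let k subjects flare and fail to stop, and let all others stop without recurrence, so q = d = 8 − k. The gap is 1 − (8 − k)/8 = k/8.

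| k | Discontinuers only, q/d | All on corticosteroids at baseline, q/n (exact 95% CI) | Gap |
|---|---|---|---|
| 0 | 8/8 = 100% | 8/8 = 100% (63% to 100%) | 0 points |
| 1 | 7/7 = 100% | 7/8 = 87.5% (47% to 99.7%) | 12.5 points |
| 2 | 6/6 = 100% | 6/8 = 75% (35% to 97%) | 25 points |
| 4 | 4/4 = 100% | 4/8 = 50% (16% to 84%) | 50 points |

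The intervals are Clopper-Pearson. The restricted figure stays at 100% in every row, whatever the number of failures to wean.

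**The case against.** The strongest case against has four parts.

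**Nothing here is tested.** Section 5.1 makes the study descriptive. There is no alpha, no success rule and no hierarchy to exploit. This stands. A reader might infer from the open list an inflated type I error, but without a hypothesis test or a nominal level no such rate can be defined.

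**The measures are tabulated anyway.** Under Section 5.1 each Part is analysed separately. CRP, NRS, pericarditis signs, MRI, PROMIS and medication changes are also pooled for Parts 3 and 5, and recurrence and Clinical Response are required outputs for the mITT population. This also stands in large part: a reader might infer that flares would vanish from the report, and they would not. What stays open is which measures are run in the prednisone-discontinued set, and which result is presented as the primary endpoint.

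**CRP is not the sole measure.** A reader might infer that the endpoint rests on CRP alone, and that CRP is unreliable because Part 2 enrols symptomatic subjects with CRP of 1 mg/dL or below that "can be attributed to concomitant medications (e.g., corticosteroids) and with pericardial inflammation present on cardiac magnetic resonance imaging (MRI) confirmed by the imaging core lab". The documents do not support this reading. Section 5.4.9.8 speaks of parameters in the plural, and the Part 2 text attributes low CRP to concomitant medication with corticosteroids as the example, whereas the subjects in question have stopped prednisone. The point reaches them only by analogy, so nothing here relies on it.

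**The rest may be elsewhere.** Section 4.3 is redacted and the protocol is not at hand, so a ranking of other endpoints may exist. But Section 4.2 is visible, and Section 1 states that the SAP's purpose is to give all details of the analysis. The weaning objective is also served by the fixed prednisone-dose summaries and the stopped category in Section 5.4.9.9. These describe weaning; they do not describe disease activity after it.

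**Conclusion.** The point holds as a matter of specification and analysis set. Followed as written, the plan reports the Parts 3 and 5 primary endpoint only in subjects who stopped prednisone, on parameters that can be chosen with results in view and that need not include recurrence. The document does not show that any such choice was made after seeing data; it only leaves room for it.

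The direction of the restriction is certain for the proportion weaned without recurrence, because q/d cannot be below q/n. Its size is not known. It equals the share of subjects who fail to wean whenever all discontinuers stay free of recurrence: 0 to 50 points across the assumed range of 0 to 4 failures among 8 subjects. The consequence is selective emphasis and an over-favourable statement about weaning in a descriptive pilot. This should be corrected, but it does not threaten the trial's other results.

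**What to change.** In Sections 4.2 and 5.4.9.8, replace the open selection with a fixed list led by one named outcome:

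- **Primary:** the number and percentage of Parts 3 and 5 subjects on corticosteroids at baseline who are off corticosteroids with no pericarditis recurrence through Visit 8, using the recurrence data of Section 5.4.9.10. Give an exact 95% CI, by Part and pooled.
- **Denominator:** all Parts 3 and 5 subjects on corticosteroids at baseline. Show as separate categories those who did not wean, flared during the taper, did not enter the EP, or have missing data.
- **Supportive, in this order:** CRP, NRS, Clinical Response.
- **Secondary:** keep the discontinuers-only summary, labelled as conditional on having stopped.

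Section 5.4.9.10 states no criteria for a recurrent episode, so the revised text should cross-refer to the definition used for those data.

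The cost is SAP wording and one extra table from data already collected, with no added procedures or subjects. The percentage will probably be less favourable and, with so few subjects, imprecise. The sponsor also gives up the freedom to choose which parameter leads.

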#### **5.4.9.9. Concomitant Pericarditis Medications**

Pericarditis medications will be identified among subjects' concomitant medications and classified as analgesics, aspirin, NSAIDs, colchicine or corticosteroids through medical review.

For the purposes of these analyses, medications taken on as needed basis (PRN) will not be accounted for due to difficulty in assessing the actual dose. Only medications with a fixed daily use frequency (QD, BID, TID, etc.) will be used, so that their daily dose can be calculated.

For the purposes of these analyses, the Treatment period ends and the Extension Period starts on the day of Visit 7 for subjects who proceed to the Extension Period. For subjects who do not enter the Extension Period, the Treatment Period ends on the day of the last study drug dose.

Each category of pericarditis medications will be analyzed for changes in the Treatment Period, Extension Period and the study as a whole as follows and categorized as follows:

1. New Medication: a new medication of the given category is taken at the end of the period compared to the start of the period.
2. Dose Increase: no new medications of the given category are taken, but the total daily dose of one of the medications increased by the end of the period compared to the start of the period.
3. Dose Decrease: there are no new medications and no dose increases, and the total daily dose of one of the medications decreased by the end of the period compared to the start of the period.
4. Stopped: a medication of the given category was taken at the start of the period, and none is taken at the end of the period.
5. Stable Dosing: none of the above.

Number and percentage of subjects with each of the above outcomes will be presented by the pericarditis medication category and study period (Treatment, Extension and study as a whole). The population will be mITT for the Treatment Period and EP for the Extension

Period and the study as a whole. The denominator for percentages for the “New Medication” outcome will be the total number of subjects in the appropriate population. For all other outcomes it will be the number of subjects who take any medication of the given category at the start of the period.

This analysis will be performed by study part, but also for pooled groups of Parts 1, 2 and 4 and Parts 3 and 5.

Use of Pain/Rescue medications will be also analysed (see section 5.4.10.7).

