**Extension Period (EP):** The EP is defined as the 18 weeks following the Treatment Period. Subjects who are considered to be “Treatment Responders” will be, at the discretion of the Investigator, offered participation in an optional 18-week EP, in which weekly administration of open-label KPL-914 may be continued for a total duration of 24 weeks. The weekly KPL-914 doses will be by self-administration or administered by adequately trained caregiver, and study nurse visits to the subject’s home as well as Investigator (or designee) telephone calls/virtual visits will continue on a monthly basis. During the EP, the Investigator is encouraged to wean concomitant NSAIDs, and/or colchicine, and/or corticosteroids. It is encouraged that NSAIDs and colchicine be tapered and withdrawn within 15 days after entry into the EP. It is encouraged that corticosteroids be progressively tapered (e.g., by 5 mg prednisone or equivalent every week in adults or 0.2mg/kg every week in subjects <18yo) and discontinued within 6 weeks after entering to EP (i.e., by Study Week 12) unless in the opinion of Investigator, a different corticosteroid weaning schedule is required based on subject’s clinical status. Other pericarditis medications may also be initiated at the discretion of the Investigator. All changes to pericarditis-related medications should be captured in the source records and eCRF

Unscheduled clinic visits can be scheduled any time as determined by the Investigator/upon subject request. In addition, Investigators are encouraged to schedule subjects at the Study Site/Clinic for an in-person Interval Evaluation Visit between Weeks 15 to 20 (8 to 13 weeks after Visit 7) to assist the Investigator in the clinical management of the subject. During this visit a physical examination, vital signs, ECG, echocardiogram, and laboratory testing can be performed. However, this visit is not mandatory, and therefore not all subjects will have it.

Subject-reported pericardial pain evaluations using a validated 11-point NRS instrument as well as AE monitoring will be performed during the EP at on-site clinic visits and/or during monthly Investigator (or designee) phone calls/virtual visits. A subject-reported QoL questionnaire will be administered at the Interval Evaluation Visit and the Final Visit of the EP. At the end of the EP, subjects will complete the Week 25/Final Visit.

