#### **5.4.2. Demographic and Baseline Characteristics**

Demographic and baseline characteristics such as age, sex, childbearing potential (for female subjects only), race, ethnicity, height (cm), weight (kg) and BMI ( $\text{kg}/\text{m}^2$ ) as well as baseline Pain Rating Scale score, whether this score is  $\geq 4$ , number of prior RIP or PPS recurrences, whether subjects are taking pericarditis medications of the following categories at baseline: analgesics, aspirin, NSAIDs, colchicine or systemic corticosteroids and number of different pericarditis medication categories at baseline will be summarized. Number of prior RIP and PPS recurrences is excluding the index and current episodes, if any, thus for Part 1, 2 and 4 will be total number of episodes minus 2 and for Parts 3 and 5, minus 1.

In addition, the following statistics will be summarized:

- Disease duration, defined as the number of years from the start of index episode to the day of signing informed consent.
- Annual incidence of episodes, defined as total number of episodes, including index, recurrence and current episodes, divided by disease duration.

The analysis will be based on the safety, PP and EP populations.

Pericarditis medications (analgesics, aspirin, NSAIDs, colchicine and corticosteroids) will be identified among subjects' prior and concomitant medications through medical review.

Descriptive statistics will be presented for age, height, weight, BMI and pain rating scale score. Frequency counts and percentage will be presented for sex, childbearing potential, race, ethnicity and use of pericarditis medications at baseline.

This analysis will be performed by study part, but also for pooled groups of Parts 1, 2 and 4 and Parts 3 and 5, and total

The demographic and baseline characteristic data will also be presented as a data listing.

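### The medication-change analysis has no category for pericarditis drugs outside five named classes, so stopping corticosteroids with such a replacement is tabulated the same as stopping without one

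*SAP*

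**What the plan says.** Section 2.2 (Extension Period) encourages investigators to wean NSAIDs, colchicine and corticosteroids. It then adds: "Other pericarditis medications may also be initiated at the discretion of the Investigator". On data capture it says: "All changes to pericarditis-related medications should be captured in the source records and eCRF".

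Section 5.4.9.9 analyses changes in pericarditis medication by period. Drugs are "classified as analgesics, aspirin, NSAIDs, colchicine or corticosteroids through medical review", with no residual group. Each outcome is judged within one category. New Medication means that "a new medication of the given category is taken at the end of the period compared to the start of the period". Stopped means that "a medication of the given category was taken at the start of the period, and none is taken at the end of the period". Only drugs with a fixed daily frequency are used; PRN drugs are left out. Section 5.4.2 uses the same five classes to describe baseline use and to count medication categories per subject.

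The primary objective of Parts 3 and 5 (Section 2.1.3) is: "To evaluate feasibility of weaning from corticosteroids while receiving KPL-914". The primary endpoint (Section 4.2) is disease activity after the corticosteroid taper. Section 5.4.9.8 addresses it through CRP and other selected efficacy parameters in "subjects who received prednisone at baseline and discontinued it by the end of EP".

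**The concern.** The design allows a treatment change that the analysis of treatment changes does not count. If a pericarditis drug outside the five classes is started, no row of the Section 5.4.9.9 table records it. A corticosteroid stop made possible by that drug then cannot be told apart, in the table, from a stop on KPL-914 without a replacement.

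The Section 5.4.9.8 subset has the same weakness: membership depends on stopping prednisone alone, so CRP measured under a replacement drug is pooled with CRP measured without one. The study is open-label with a single arm, so no control group would reveal the difference. What is at stake is how the Parts 3 and 5 weaning result can be read.

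**Working it through.** The plan states no figure for this point, and Section 3.1 sets the sample size empirically, so there is nothing to reproduce. The check is to apply the Section 5.4.9.9 rules to hypothetical subjects, first with the five stated categories and then with a sixth for other pericarditis medication.

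| Subject (start to end of period) | Five stated categories | With a sixth category |
|---|---|---|
| (a) Prednisone, then nothing | Corticosteroids: Stopped | Unchanged |
| (b) Prednisone, then only a drug outside the five classes | Corticosteroids: Stopped | Corticosteroids: Stopped; other: New Medication |
| (c) Prednisone unchanged, drug outside the five classes added | Corticosteroids: Stable Dosing | Corticosteroids: Stable Dosing; other: New Medication |
| (d) Prednisone, then colchicine at a fixed daily frequency | Corticosteroids: Stopped; colchicine: New Medication | Unchanged |

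(In (a), (b) and (d) the wording of Dose Decrease is met as well as Stopped. This does not affect the comparison.)

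Under the plan, (a) and (b) are identical, and the addition in (c) is not shown. Case (d) is shown, so the table reveals replacement by some drugs and not by others.

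Next, the effect on a rate. Let n be the subjects on corticosteroids at the start of the period, s those who stop, and r those among the s who start a drug outside the five classes.

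- Plan's Stopped rate: s/n.
- Rate of stopping without such a replacement: (s − r)/n.
- Difference: s/n − (s − r)/n = r/n, which is never negative.

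For r = 1 the difference is 1/10 = 10 percentage points when n = 10, and 1/20 = 5 points when n = 20. As an illustration only (assumed values n = 10, s = 10, r = 2), the table would show 10/10 stopped and no new medication for these subjects, while stops without replacement would be (10 − 2)/10 = 8/10. The SAP gives neither n nor r. Section 3.1 foresees up to about 40 subjects across all five Parts, so n will be small.

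Finally, the other outputs. Section 5.4.6 summarises all concomitant drugs by ATC class and preferred term and lists them by subject with dates, frequency and indication. The summary gives no start-to-end change by period and no link to corticosteroid stopping; the listing allows a manual check but gives no count. Section 5.4.10.7 has an other type, but for pain/rescue medication only.

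**The case against.** The strongest reply is that little is lost. The Section 5.4.6 listing carries indication and start and stop dates, so in a descriptive pilot of this size a reader could find one or two such subjects. This stands: a reader might infer that these drugs vanish from the report, and they do not. They are missing only from the medication-change table and from any count tied to corticosteroid stopping.

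A reader might also infer that any switch of drug class is hidden. It is not: a move to a fixed-frequency drug in another of the five classes shows as New Medication, as in (d).

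The scope of other medications in Section 2.2 is also open. The phrase follows NSAIDs, colchicine and corticosteroids, so it could partly mean analgesics or aspirin, which are covered. The SAP names no sixth class, and the protocol, which might limit them, is not at hand. This limits what can be said about size. It does not close the gap, because nothing in the SAP confines the phrase to those two.

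A general one-way bias in the medication analysis is not supported either. A subject who takes an out-of-class drug at baseline and stops it is uncounted too, which understates overall weaning. The fixed direction applies only to corticosteroid stops.

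Lastly, the Stopped row is correct as labelled and makes no claim about substitution, and Section 5.4.9.10 separately counts recurrences, including one that prompted a new drug. Both are true. But the objective concerns weaning while on KPL-914, and the Section 5.4.9.8 subset has no condition on replacement, so the distinction matters to that reading.

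**Conclusion.** The point holds as a tabulation gap that bears on the Parts 3 and 5 primary question. Followed exactly, the plan gives the same tabulated result to a subject who replaces corticosteroids with a drug outside the five classes and to one who stops without replacement, and it pools both in the discontinuer analysis.

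For the count of corticosteroid stops the direction follows from the arithmetic: the excess r/n is zero or positive, so weaning can only look more feasible. For CRP in the discontinuers, a favourable shift rests on the assumption that the added drug lowers disease activity. The size cannot be estimated, because the SAP gives neither the drugs nor their expected frequency; it may be nil. The information remains recoverable from the Section 5.4.6 listing. The change should be made because it is cheap and affects how a primary result is read.

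**What to change.** 1. Add a category for other pericarditis medication, identified by medical review of indication, to Sections 5.4.9.9 and 5.4.2.
2. Count starts in this category whatever the dosing frequency. Under the present fixed-daily-frequency rule, a drug not given daily would still drop out.
3. Report the corticosteroid Stopped row and the Section 5.4.9.8 discontinuer analysis with and without a newly started or increased pericarditis medication. This links starts and stops within subjects, which separate rows per category do not.

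The cost is SAP wording, one more category in a medical review that is already planned, and a split of two planned outputs. No new data are needed, since Section 2.2 already asks for all changes in pericarditis-related medication to be recorded.
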